## 7.2 Sample Size

For each of the primary conspicuity endpoints, the objective is to estimate the ability of each imaging method (T2 weighted MRI, CEST MRI, Adv Diff, and DESE DSC) at identifying brain metastases at baseline. Standard of care qualitative T1 post-contrast imaging will be considered the gold standard. Each patient will have between 1 and 10 lesions, with an expected average of 4 lesions per patient. (For patients with more than 10 lesions, 10 will be chosen as described in Section 5.1.4.1.) The primary analysis will consider the largest lesion within each patient, and the analysis will be repeated considering all lesions. The sensitivity will be calculated along with the corresponding 95% confidence interval. With 50 patients, this confidence interval will be no wider than 14.5% on either side of the estimated proportion. The confidence interval around the proportion of total lesions detected will be tighter, depending on the total number of lesions.

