## 2 BACKGROUND

### 2.1 Brain Metastasis

Brain metastases have been reported to occur in up to 30% of patients with cancer, and treatment options include supportive care, surgery, and radiotherapy. The incidence of brain metastases is increasing, partly because of increase in the incidence of primary cancers and partly because improvements in treatment options have prolonged survival of patients with cancer, which increases the chance of primary tumors metastasizing. There are very few chemotherapy options open to patients with brain metastases. Stereotactic radiosurgery (SRS) has become an increasingly important treatment option for the initial management of patients with brain metastases. Early and accurate detection of small metastases is associated with improved treatment success. At present, gadolinium-enhanced MRI is considered to be the imaging technique of choice in patients suspected of brain metastases.

Significant limitations to the utilization of gadolinium-enhanced MRI in the screening for brain metastasis is cost and the requirement of an intravenous injection of a contrast agent. Some patients have claustrophobia requiring sedation. Additionally, underlying conditions, such as back pain, may make it hard for the patients to lie still for the duration of the MRI. Achieving standard-of-care MR imaging in these populations can be challenging. There is a vital clinical necessity for a safe and efficient screening imaging technology to offer patients at risk of brain metastases, who have contraindications to gadolinium as well as the ability to tolerate long examination times. Thus, fruitful diagnostic techniques that do not rely on gadolinium injection would be clinically meaningful by improving cost, time and safety of MR imaging.

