## 3.3 NUMBER OF PARTICIPANTS

Fifty (50) patients will be studied.

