## 7.3 Analysis Plan

Patients are expected to have on average four brain lesions each. The primary analysis will be performed on the largest lesion within patients at baseline, and secondary analyses will consider all lesions. The sensitivity of each method at detecting lesions as determined by T1 weighting will be reported with 95% confidence intervals. Analyses will also be performed at the subsequent scans as numbers permit.

For the secondary endpoints that consider treatment response, for each of the imaging methods, at each time point, we will calculate the contrast to noise ratio (CNR) in patients with lesions that respond to treatment and in patients with local failure and will compare these by using a Wilcoxon rank-sum test. If numbers permit, analyses may be repeated using all lesions. Additionally, of the lesions that initially respond, some will subsequently grow in size after the initial response. Of these, some will be considered treatment change and some residual disease. The CNR will be compared between lesions with treatment change and those that are progressive disease using a Wilcoxon rank-sum test.

All statistical tests will be performed with two-sided tests with 5% Type I error rates. No adjustment will be made for the multiplicity of testing. We recognize that the Type I error rate overall will be greater than 5%.

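### The primary sensitivity describes only each patient's largest lesion, and the all-lesion repeat has neither a size breakdown nor an allowance for within-patient clustering

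*Combined protocol and SAP*

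**What the plan says.** Section 3.3 fixes the sample: "Fifty (50) patients will be studied". Section 7.2 expects several lesions in most of them: "Each patient will have between 1 and 10 lesions, with an expected average of 4 lesions per patient". The primary estimate uses one lesion per patient: "The primary analysis will consider the largest lesion within each patient, and the analysis will be repeated considering all lesions". Section 7.3 confirms the ranking: "The primary analysis will be performed on the largest lesion within patients at baseline, and secondary analyses will consider all lesions". Section 1.2.1 lists per-lesion conspicuity at baseline and follow-up among the secondary objectives.

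The result is an estimate with an interval: "The sensitivity will be calculated along with the corresponding 95% confidence interval". Its precision is given as "With 50 patients, this confidence interval will be no wider than 14.5% on either side of the estimated proportion". For the all-lesion repeat, 7.2 gives no figure and says only: "The confidence interval around the proportion of total lesions detected will be tighter, depending on the total number of lesions".

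The primary objectives in 1.1.1 and the aim in 7.2 concern brain metastases at baseline, with no restriction to the largest. Section 2.1 adds: "Early and accurate detection of small metastases is associated with improved treatment success". No section gives a reason for choosing the largest lesion, plans sensitivity by lesion size, or names a method for correlated lesions.

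**The concern.** There are two gaps.

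**Target.** The question asked is how well each method finds brain metastases; the question answered first is how well it finds the largest one in each patient. If larger lesions are easier to find, the second figure is higher. A method that often misses small lesions could then show a good primary result, although small lesions are part of the stated rationale. The all-lesion repeat mixes sizes, so it would not show where a method stops working.

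**Precision of the repeat.** Lesions in one patient share the scanner session, the primary tumour and the patient's physiology, so their detection outcomes are likely to be correlated. An interval that treats about 200 lesions as independent would be too narrow, and section 7.2 invites that calculation by linking precision to the lesion count alone.

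**Working it through.** **Inputs from the documents.** 50 patients (3.3); mean of 4 lesions, range 1 to 10 (7.2); 95% interval (7.2); stated half-width at most 14.5 points (7.2). The documents give no ICC, no spread of lesion counts, no lesion-size distribution and no relation between size and detection. Values for these below are assumptions.

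**1. The plan's own figure.** The exact (Clopper-Pearson) 95% interval at 25/50 is 35.5% to 64.5%, a half-width of 14.47 points. This reproduces the stated 14.5. The Wald half-width is 1.96 × √(0.25/50) = 13.9 points.

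**2. Share of lesions in the primary estimate.** Expected lesions: 50 × 4 = 200. Primary: 50. Outside the primary: 1 − 50/200 = 75%.

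**3. Gap between largest-lesion and all-lesion sensitivity.** Let d be the sensitivity in largest lesions minus that in the others. Largest lesions are one quarter of the total, so the gap is 0.75 × d.

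| Assumed d | Gap (points) |
|---|---|
| 0 | 0 |
| 0.05 | 3.75 |
| 0.10 | 7.5 |
| 0.20 | 15 |
| 0.30 | 22.5 |

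Example: 95% in largest and 75% in other lesions gives (95 + 3 × 75)/4 = 80% over all lesions. From d of about 0.20 upward, the gap exceeds the stated half-width.

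**4. The gap under assumed detection curves.** A simulation of 200,000 patients per setting assumed:
- 1 to 10 lesions per patient, mean 4, coefficient of variation (cv) about 0.66
- lognormal diameters truncated below 5 mm, median 7 or 11 mm before truncation, log-SD 0.4 to 0.6
- logistic detection, slope 0.6 per mm, reaching 50% at 6 or 8 mm

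Results across settings:
- largest-lesion sensitivity: 74% to 96%
- all-lesion sensitivity: 51% to 88%
- sensitivity in lesions up to 10 mm: 39% to 73%
- gap, largest minus all: 8 to 24 points
- lesions up to 10 mm: 11% to 42% of the primary lesions, 38% to 77% of all lesions

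The extremes do not all occur together. The 96% figure arises with 50% detection at 6 mm and a median of 11 mm, where lesions up to 10 mm are found about 70% of the time.

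**5. Precision of the all-lesion repeat.** With mean m = 4 lesions per patient, the design effect is 1 + (m × (1 + cv²) − 1) × ICC. With cv = 0.66 this is 1 + (4 × 1.4356 − 1) × ICC = 1 + 4.74 × ICC. Effective n is 200 divided by the design effect, and the half-width at p = 0.5 is 1.96 × √(0.25/effective n).

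| Assumed ICC | Design effect | Effective n | Half-width (points) |
|---|---|---|---|
| 0 (clustering ignored) | 1.00 | 200 | 6.9 |
| 0.1 | 1.47 | 136 | 8.4 |
| 0.3 | 2.42 | 83 | 10.8 |
| 0.5 | 3.37 | 59 | 12.7 |
| 0.63 | 3.99 | 50 | 13.8 |

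The gain over 50 single lesions (Wald 13.9 points) disappears when the design effect reaches 200/50 = 4, that is at ICC = 3/4.74, or about 0.63. With exactly 4 lesions in every patient (cv = 0), the half-widths are 7.9, 9.6 and 11.0 points at ICC 0.1, 0.3 and 0.5, and an ICC of 1 is needed to lose the gain.

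**The case against.** The choice of the largest lesion is defensible. One lesion per patient gives independent observations and a valid binomial interval; the stated precision reproduces; and the estimate is unbiased for the target that 7.2 and 7.3 both name. A patient-level figure also suits the screening interest in 2.1. All of this stands.

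Making the all-lesion figure primary would have costs. Precision would depend on an unknown ICC, and patients with many lesions would carry more weight. For patients with more than ten lesions, the set would follow the caudal and cranial selection rule in 5.1.4.1. The case for swapping the headline is therefore a trade-off, and I do not press it.

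Two stronger readings are tempting. A reader might infer that three-quarters of the lesions are discarded. They are not: 7.2, 7.3 and 1.2.1 all provide for an analysis of all assessed lesions, and the 75% lie outside the primary estimate only. A reader might also infer that the primary figure overstates detection. The documents do not establish that, because they give neither a size gradient nor an explicit rule for calling a lesion detected. The gap could be zero.

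The objection does not answer three points: the objective is worded more broadly than the primary estimate, no analysis by size is planned, and no method is given for clustered lesions.

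**Conclusion.** The concern holds in a limited form. The primary sensitivity is sound as a statement about the largest lesion per patient, about 50 of 200 expected lesions. It does not extend to brain metastases in general or to small ones. Any excess over per-lesion sensitivity depends on an assumed size gradient: 8 to 24 points under the curves above, zero without a gradient.

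The statement that the all-lesion interval will be tighter is conditional. Against a naive half-width of about 6.9 points, allowing for clustering gives about 8.4 to 12.7 points at ICC 0.1 to 0.5 with cv 0.66, and no gain above an ICC of about 0.63. The ICC and cv are assumptions, and p = 0.5 is the least precise case.

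This is a matter of labelling and of completing the secondary analysis. It does not invalidate the primary analysis or the sample size.

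**What to change.** In sections 7.2 and 7.3:

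1. Keep the largest-lesion analysis as primary, and label the result *sensitivity for the largest lesion* wherever it is reported.
2. Report the all-lesion sensitivity beside it for each method, with an interval that respects the patient as the cluster: a bootstrap resampling patients, or GEE with robust standard errors.
3. Break the all-lesion figure down by baseline longest diameter, 5 to 10 mm and above 10 mm, using the measurements already taken under 5.1.2. Sections 3.1 and 5.1 do not clearly say whether additional lesions under 5 mm are assessed; if they are, add a row for them.
4. Replace the sentence on the tighter all-lesion interval with a statement that its precision depends on the number of lesions, their spread over patients and the within-patient correlation.

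The cost is SAP wording and two more table rows per method, with no new data. The all-lesion interval will be wider than the naive one, and the size subgroups will be imprecise and should be presented as descriptive.

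### If the 14.5% precision bound in Section 7.2 comes from the exact (Clopper-Pearson) interval, as it appears to, it is slightly too small: one side can reach 14.83 points

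*Combined protocol and SAP*

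**What the plan says.** Section 3.3 sets the sample size: "Fifty (50) patients will be studied". Section 7.2 fixes the unit of the primary analysis: "The primary analysis will consider the largest lesion within each patient, and the analysis will be repeated considering all lesions". It then says "The sensitivity will be calculated along with the corresponding 95% confidence interval", followed by the precision statement "With 50 patients, this confidence interval will be no wider than 14.5% on either side of the estimated proportion". Section 7.3 repeats the reporting plan: "The sensitivity of each method at detecting lesions as determined by T1 weighting will be reported with 95% confidence intervals". Neither section names the method for the interval or gives an expected sensitivity for any imaging technique. Section 7.2 contains no hypothesis, power calculation or target precision, so this sentence is the only quantitative support for the number of patients.

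**The concern.** The sentence is a worst-case claim about each arm of the interval, whatever sensitivity is observed. For a symmetric interval, such as the simple normal-approximation (Wald) interval, both arms are longest at 50%, so evaluating at 50% gives a valid bound. An exact interval behaves differently. Away from 50% one arm shortens and the other lengthens for a while, so 50% is the worst case for total width but not for each arm. If 14.5% was obtained from the exact interval at 50%, the bound fails over part of the range.

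At stake is the accuracy and reproducibility of the one figure that supports the sample size, and the absence of a named method for the primary estimates.

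**Working it through.** **Inputs**
- n = 50, from Section 3.3. One lesion per patient in the primary analysis (Section 7.2), so 50 independent yes/no outcomes, assuming that every patient contributes a baseline result.
- Confidence level 95%, from Section 7.2. I take it as two-sided with 2.5% in each tail, in line with Section 7.3: "All statistical tests will be performed with two-sided tests with 5% Type I error rates".
- Stated bound: 14.5 percentage points on either side (Section 7.2).
- Interval method: not given, so inferred in step 1.

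**Step 1. Reproduce 14.5%.** With x detected out of n, the Clopper-Pearson limits are
- lower = 2.5% quantile of Beta(x, n − x + 1)
- upper = 97.5% quantile of Beta(x + 1, n − x)

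At x = 25 these are 35.53% and 64.47%, so each arm is 50 − 35.53 = 64.47 − 50 = 14.47 points, which rounds to 14.5.

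The Wald arm at 25/50 is 1.96 × √(0.25/50) = 13.86 points. All the methods tried:

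| Method | Arm at 25/50 | Longest arm over all x |
|---|---|---|
| Clopper-Pearson | 14.47 | 14.83 |
| Wald | 13.86 | 13.86 |
| Wald, t quantile and n − 1 | 14.35 | 14.35 (symmetric, so longest at 50%) |
| Wald, continuity-corrected | 14.86 | 14.86 |
| Wilson | 13.36 | 13.86 |
| Wilson, continuity-corrected | 14.28 | 14.86 |
| Agresti-Coull | 13.36 | 13.89 |
| Jeffreys | 13.53 | 13.83 |
| Inverted binomial test | 14.12 | 14.15 |

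Only Clopper-Pearson gives 14.5 at 25/50.

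**Step 2. Apply the same method to every possible result, x = 0 to 50.** Selected rows, in percentage points:

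| x/50 | Observed | Lower arm | Upper arm | Half of total width |
|---|---|---|---|---|
| 25 | 50% | 14.47 | 14.47 | 14.47 |
| 26 | 52% | 14.58 | 14.34 | 14.46 |
| 28 | 56% | 14.75 | 14.01 | 14.38 |
| 31 | 62% | 14.83 | 13.35 | 14.09 |
| 33 | 66% | 14.77 | 12.79 | 13.78 |
| 35 | 70% | 14.61 | 12.14 | 13.37 |
| 36 | 72% | 14.49 | 11.77 | 13.13 |
| 40 | 80% | 13.72 | 9.97 | 11.84 |
| 45 | 90% | 11.81 | 6.67 | 9.24 |

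At 31/50 the interval is 47.17% to 75.35%, so the lower arm is 62 − 47.17 = 14.83. The table mirrors below 50%: at 19/50 the upper arm is 14.83.

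**Step 3. Compare with the stated bound.** The longer arm is above 14.5 at 26/50 to 35/50 (lower side) and at 15/50 to 24/50 (upper side). That is 10 + 10 = 20 of the 51 possible results. The largest excess is 14.83 − 14.5 = 0.33 points, or 0.33/14.5 ≈ 2% of the stated figure. Half of the total width peaks at 14.47, at 25/50.

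**The case against.** The strongest reply is that the documents do not say which interval will be used, so the bound cannot be called wrong outright. This stands. Under Wald, Wilson, Agresti-Coull, Jeffreys or the inverted binomial test, no arm exceeds 14.15 points and the sentence is true, if loose. The criticism is therefore conditional on the exact method. The inference is a good one, since no other method tried yields 14.5, but it remains an inference.

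A second reply is that quoting the half-width at 50% is ordinary planning shorthand, and as a half-width 14.5% is a correct maximum. This softens the point without removing it, because the sentence makes its claim for each side.

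A third reply is that the excess has no consequence. This also stands. The primary aims are estimation, and Sections 7.2 and 7.3 set no precision target or success threshold that 14.8 would miss and 14.5 would meet.

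A reader might go further in three ways that the documents do not support:
- That 50 patients are too few. A difference of 0.33 points gives no ground for this.
- That the affected range of 52% to 70% is where the results will fall. The plan states no expected sensitivity for any technique, so nothing can be said about which results are likely.
- That the analyst will use Wald and report intervals with poor coverage near 100%. Nothing in 7.2 or 7.3 points to Wald, and the plan's own figure points away from it, since Wald gives 13.86.

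**Conclusion.** The concern holds in a conditional and minor form. If the interval is exact, as the figure indicates, the stated limit of 14.5 points on either side is exceeded by up to 0.33 points at observed sensitivities of 30% to 48% and 52% to 70%. It holds at 50%, at 28% and below, and at 72% and above. The conclusion assumes 50 evaluable patients, one lesion each, and a two-sided 95% Clopper-Pearson interval. It does not affect the sample size, the design or the estimand. What needs correcting is the wording of one figure and the omission of the method that produced it.

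**What to change.** In Section 7.2, name the exact (Clopper-Pearson) 95% interval and state that it will be no wider than 15 percentage points on either side of the estimate (true maximum 14.83). In Section 7.3, name the same method for the reported sensitivities. If the sponsor intended another method, name that one in both sections and replace 14.5% with its own maximum from the first table above. The cost is one sentence in each section, with no change to the number of patients, the procedures or the data collected.

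### Per-lesion sensitivity intervals make no allowance for several lesions in the same patient, so they would be too narrow

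*Combined protocol and SAP*

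**What the plan says.** Section 7.2 sets the data structure: "Each patient will have between 1 and 10 lesions, with an expected average of 4 lesions per patient". It then fixes the units of analysis: "The primary analysis will consider the largest lesion within each patient, and the analysis will be repeated considering all lesions". For 50 patients it gives a 95% interval of at most 14.5 points either side. For the repeat on lesions it says: "The confidence interval around the proportion of total lesions detected will be tighter, depending on the total number of lesions".

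Section 7.3 agrees on the units ("The primary analysis will be performed on the largest lesion within patients at baseline, and secondary analyses will consider all lesions") and on reporting: "The sensitivity of each method at detecting lesions as determined by T1 weighting will be reported with 95% confidence intervals". Objectives 1.2.1.1 to 1.2.1.4 make per-lesion conspicuity a secondary aim for each method, at baseline and at follow-up.

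For regrowing lesions, 7.3 plans a test on lesions: "The CNR will be compared between lesions with treatment change and those that are progressive disease using a Wilcoxon rank-sum test". The comparison of responders with local failures is worded by patient, with an optional extension: "If numbers permit, analyses may be repeated using all lesions". The error rate is stated as follows: "All statistical tests will be performed with two-sided tests with 5% Type I error rates". The only caveat on that rate concerns multiplicity.

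Nowhere do the documents mention within-patient correlation, a design effect, a robust variance, a mixed model, a bootstrap by patient or a clustered rank test.

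**The concern.** Lesions in one patient share the primary cancer, the scan session and the contrast dose. If a method shows one of them, it is more likely to show the others. The information in 200 lesions from 50 patients is then less than that in 200 independent lesions. It depends on the number of patients, the spread of lesion counts and the within-patient correlation as well as on the lesion total.

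Section 7.2 ties precision to the lesion total alone and describes the all-lesion analysis as a repeat of the one-lesion-per-patient analysis. An analyst who follows that text puts a binomial interval on lesions. The reported per-lesion sensitivities would then look more precise than they are, for every method and time point. An ordinary rank-sum test on lesions rests on the same independence assumption.

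**Working it through.** **Inputs from the documents.** 50 patients (3.3, 7.2); 1 to 10 lesions each, mean 4 (7.2); 95% intervals (7.2, 7.3); 14.5 points (7.2).

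**Assumptions, not in the documents.** ICC of 0.1, 0.3 or 0.5. Coefficient of variation (CV) of lesion counts of 0 (equal counts) or 0.657, the latter from a decreasing distribution on 1 to 10 with mean 4. Widths are at 50% sensitivity, where they are largest.

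**1. The plan's own figure.** The exact binomial interval for 25/50 is 35.5% to 64.5%; (64.5 − 35.5)/2 = 14.5. The simple normal formula gives 1.96 × √(0.25/50) = 13.9. The plan's figure is therefore the exact half-width, and it stands.

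**2. All lesions taken as independent.** 50 × 4 = 200. The exact half-width at 100/200 is 7.1 points (normal formula 6.9).

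**3. With clustering.** Design effect DE = 1 + [(1 + CV²) × 4 − 1] × ICC, and effective n = 200/DE. The bracket is 3 for CV 0, and 1.4314 × 4 − 1 = 4.726 for CV 0.657.

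| ICC | CV 0: DE / effective n / half-width | CV 0.66: DE / effective n / half-width |
|---|---|---|
| 0.1 | 1.30 / 154 / 8.2 | 1.47 / 136 / 8.7 |
| 0.3 | 1.90 / 105 / 9.9 | 2.42 / 83 / 11.2 |
| 0.5 | 2.50 / 80 / 11.4 | 3.36 / 60 / 13.3 |
| 1.0 | 4.00 / 50 / 14.5 | 5.73 / 35 / 17.3 |

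The lesion interval stops being tighter than the patient interval when effective n falls to 50, that is when DE = 4. This happens at ICC = 3/4.726 = 0.63 for CV 0.66, at 3/4 = 0.75 for CV 0.5, and only at 1 for equal counts.

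**4. Coverage of the unadjusted exact interval on lesions.** Simulation: 50 patients, CV 0.66, beta-binomial detection, 10,000 runs.

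| True sensitivity | ICC 0.1 | ICC 0.3 | ICC 0.5 |
|---|---|---|---|
| 50% | 91% | 80% | 74% |
| 80% | 90% | 82% | 73% |
| 95% | 92% | 83% | 75% |

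Repeat simulations agree to within about a point, so the ranges are about 89-92%, 79-84% and 73-75%. For equal counts, the approximation 2Φ(1.96/√DE) − 1 gives 91%, 84% and 78%.

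**5. Ordinary rank-sum test, true null, nominal 5%.** 6,000 runs, 30% of lesions in one group, the same ICC in CNR and in the group label, Monte Carlo standard error about 0.3 points.

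| Lesions entering | ICC 0.1 | ICC 0.3 | ICC 0.5 |
|---|---|---|---|
| All (optional repeat) | 5.5% | 7.7% | 13.7% |
| 30% (regrowth) | 4.8% | 6.0% | 7.0% |
| 20% (regrowth) | 4.8% | 5.1% | 6.7% |

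In the same runs, the Datta-Satten clustered rank-sum test stayed between 4.5% and 5.6%.

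**6. A candidate interval.** This is an exact interval on effective n, with DE estimated from patient-level residuals, floored at 1, and a t correction with 49 df. At ICC 0.1/0.3/0.5 it covers 96/96/96% at 50% sensitivity and 96/94/92% at 95% sensitivity. Its mean half-widths at 50% sensitivity are 8.8/11.3/13.4 points. At 95% sensitivity, Wilson on effective n covers 95/92/90% and a symmetric cluster-robust interval 91/87/84%. If every lesion is detected, the lower exact limit is 0.025^(1/n): 98.2% for 200/200 and 92.9% for 50/50.

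**The case against.** The strongest reply is that the plan already protects what matters most. The primary analysis takes one lesion per patient, so clustering cannot enter it, and its 14.5 points reproduce. No interval method is named for lesions, so a statistician could adjust without contradicting the text. At ICC 0.1 the half-width moves only from 7.1 to between 8.2 and 8.7 points. All of this stands, and it limits the point to secondary analyses. It does not remove it: the only precision rule given depends on the lesion count alone, the only lesion-level test named is the ordinary one, and an adjustment chosen later would be chosen after seeing the data.

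A reader might infer more than the documents support:
- **That the claim of a tighter interval is false.** It holds at low to moderate correlation and fails only above an ICC of about 0.63 at CV 0.66. It is not guaranteed, but it is not shown to be wrong.
- **That the planned tests are badly inflated.** The regrowth test shows about 5-7%. The marked figure, about 14%, needs ICC 0.5 in both CNR and label and belongs to a repeat that 7.3 makes conditional. The patient-worded comparison is not affected.
- **That the largest lesion is undefined when a patient has more than ten.** Section 5.1.4 limits assessment to ten, and 7.2 refers to that selection just before naming the largest lesion, so the natural reading is the largest of those assessed. Because 5.1.4.1 selects by position, an explicit phrase would help, but that is a clarification only.

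**Conclusion.** The point holds for the per-lesion sensitivity intervals under objectives 1.2.1.1 to 1.2.1.4 and should be fixed. As the plan is written, these intervals would carry a 95% label and cover less whenever detection is positively correlated within patients. In the illustration, coverage falls to roughly 90% at ICC 0.1, 80% at 0.3 and 74% at 0.5. The direction needs no assumption beyond a positive correlation. The size rests on the assumed ICC and spread of lesion counts, and on 200 lesions, which is the plan's expected mean times 50. The lesion-level rank-sum tests are a lesser part of the same gap. Nothing here weakens the primary analysis.

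**What to change.** **Section 7.2.** Replace the last sentence with: *The interval for all lesions will allow for clustering within patient; its width depends on the number of patients, the lesions per patient and the within-patient correlation.*

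**Section 7.3, intervals.** Report lesion-level sensitivities with a patient-clustered 95% interval suited to proportions near 100%. An exact interval on the design-effect-adjusted effective sample size is one option; note that its simulated coverage drops to about 92% at 95% sensitivity and ICC 0.5. If a method detects every lesion, the correlation cannot be estimated; use the number of patients as the effective size. This is a cautious convention rather than a strict worst case, since with unequal counts effective n can fall below 50.

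**Section 7.3, tests (lesser).** Use a clustered rank-sum test for CNR comparisons made on lesions.

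**Sections 5.1.4 and 7.2 (clarification).** If it is what is intended, state that the largest lesion means the largest of those assessed under 5.1.4 and 5.1.4.1.

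**Cost.** A few sentences and some analysis work, with no extra patients, scans or measurements. The downside is wider lesion-level intervals; the exact effective-n version is also slightly conservative when lesions are in fact independent (about 97% coverage).
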